5.2.2 Plasma infusion day

Patients randomized to the treatment arm will need to be seen on the day of infusion which should occur within 48 hours of randomization and be within 96 hours of symptom onset.

Study plasma administration will be allowed for the Control arm after hospital admission if requested by the patient's medical team.

- On the day of infusion, blood will be drawn for:
 1. Inflammatory markers

- a. D-Dimers
 - b. Ferritin
 - c. CRP
- 2. Serological testing: anti-SARS CoV-2 titers
- 3. Exploratory blood test for genomics (optional)
- 4. Exploratory blood test for cytokines/chemokines (optional)
- 5. Rectal swab for gut microbiome analyses, to be sent to the CDI if possible
- 6. CBC
- 7. Complete chemistry
- 8. ABO Rh

- Procedure:
 - 1. A single unit of approximately 400-500 mL of liquid fresh plasma or 2 units of fresh frozen plasma for a total of approximately 400 mL will be transfused at an approximate rate of 50 mL per hour x 30 minutes, then the rate may be increased up to 150 mL per hour until completion. If plasma availability does not allow for 2 units of FFP, a single unit may be administered.
 - 2. If possible, 10mL of plasma will be collected for research from the infusion line and sent to the CDI
 - 3. The infusion may be slowed or stopped as per investigator's decision for minor transfusion reactions only. The transfusion will be discontinued for any transfusion reactions other than minor allergic reactions.
 - 4. An investigation will be initiated when there are signs of a systemic transfusion reaction.
 - 5. Premedication 30 – 60 minutes prior to the infusion will include 100 mg hydrocortisone IV and may include acetaminophen 650 mg PO and diphenhydramine 25 mg IV. Diphenhydramine 25 mg IV and hydrocortisone 100 mg IV may be repeated as needed for an infusion reaction at the discretion of the investigator.
 - 6. Vitals signs should be monitored following Hackensack Meridian Health Blood and Blood Product Administration SOP guidelines:
 - a. Temperature, pulse, respirations, and blood pressure pre-infusion (within 30 minutes), 15 minutes after the start, every hour during, if a transfusion reaction is suspected or if there is any change in patient condition, post transfusion (5-15 minutes post)

5.2.3 Post enrollment day +3 and day +7 (or closest working day). May be done remotely.

- COVID-19 symptom screen by telephone (Y/N)
 - 1. Fever (T max)
 - 2. Cough
 - 3. Shortness of breath
 - 4. Ageusia and/or anosmia
 - 5. Myalgias
 - 6. Headaches
 - 7. Other symptoms that the patient attributes to their COVID-19 infection

- New medical conditions, AE evaluation
- Safety assessment
- Rectal swab for microbiome at day +3 and day +7 to be sent to the CDI if possible.

5.2.4 Post enrollment: 2 weeks (+/- 3 days), 4 weeks and 2 months (+/- 5 days). Preferably in person.

- COVID-19 symptom screen (Y/N)
 1. Fever (T max)
 2. Cough
 3. Shortness of breath
 4. Ageusia and/or anosmia
 5. Myalgias
 6. Headaches
 7. Other symptoms that the patient attributes to their COVID-19 infection
- New medical conditions, AE evaluation
- Safety assessment
- Serological testing: anti-SARS CoV-2 titers if possible.
- Swab for COVID-19 testing at 2 weeks, and again at 4 weeks if week 2 is positive.
- Exploratory blood test for cytokines/chemokines at +2 and +4 weeks to be sent to the CDI if possible.
- Rectal swab for microbiome at +2 weeks, +4 weeks, and +2 months to be sent to the CDI if possible.

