- Immunosuppressive medications except for prednisone (or steroid equivalent) \geq 10 mg daily.
- Performance status $<$ 50 by KPS
- Pneumonia by radiographic evaluation

Treatment Plan

Plasma collection

Collection of plasma will be performed on eligible and suitable donors meeting regulatory requirements (Appendix A).

SARS-CoV-2 convalescent plasma consisting of 1 unit of approximately 400-500 mL or 2 units of approximately 200 mL will be collected by apheresis from a volunteer donor who recovered from COVID-19 infection and was found to have anti-SARS-CoV2 titers $\geq 1:500$.

Donors may be referred to an outside licensed Blood Center for plasmapheresis to be performed as per the licensed Blood Center SOPs.

Convalescent plasma collected under IND 19824 may be used.

Plasma infusion

Approximately 400-500mL of liquid fresh or fresh frozen plasma will be infused one time.

Statistical Analysis

This is a randomized phase II trial to assess the efficacy and safety of treatment with convalescent plasma infusion (Treatment) versus without convalescent plasma infusion (Control) in patients with early COVID-19 infection at high-risk of admission. Eligible subjects will be stratified randomized by their Charlson Comorbidity Index scoring in a 1:1 ratio to receive either Treatment or Control (8.4). For this trial, we have considered a group sequential design which has more interim analyses and utilized a three-stage O'Brien-Fleming design.²³

The first stage analysis will be after 51 subjects in each arm, that is after a total of 102 subjects. If the Z statistic is greater than or equal to 0.179 (p-value ≥ 0.571), the hypothesis H_0 is accepted and the trial stops, we conclude the Treatment is not worth pursuing; if the Z statistic is less than or equal to -2.849 (p-value ≤ 0.002), the hypothesis H_0 is rejected and early evidence for promising efficacy is established. Otherwise, the trial continues to the next stage.

The second stage analysis will be after 102 subjects in each arm, that is after a total of 204 subjects. If the Z statistic is greater than or equal to -0.944 (p-value ≥ 0.173), the hypothesis H_0 is accepted and the trial stops, we conclude the Treatment is not worth pursuing; and if the Z statistic is less than or equal to -2.015 (p-value ≤ 0.022), the hypothesis H_0 is rejected and early evidence for promising efficacy is established. Otherwise, the trial continues to the final stage.

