3.2 Patient

- Patient age ≥ 30 years old, newly diagnosed with a COVID-19 infection with onset of first symptoms ≤ 96 hours, and least one other high-risk feature:
 1. Age ≥ 65
 2. BMI 30 or above
 3. Hypertension, defined as SBP above 140 or DBP above 90, or requiring medication for control.
 4. Coronary artery disease (history, not ECG changes only)
 5. Congestive heart failure
 6. Peripheral vascular disease (includes aortic aneurysm ≥ 6 cm)
 7. Cerebrovascular disease (history of CVA or TIA)
 8. Dementia
 9. Chronic pulmonary disease
 10. Liver disease (such as portal hypertension, chronic hepatitis)
 11. Diabetes (excludes diet-controlled alone)
 12. Moderate or severe renal disease defined as having a GFR <60 mL/min
 13. Cancer (exclude if ≥ 5 year in remission)
 14. AIDS (not just HIV positive)

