5.2 Patient procedures and evaluation (see Appendix B)

Patients may be screened, enrolled and randomized remotely. The day of randomization will be designated as day 0 for both Treatment and Control groups. Patients randomized to the treatment arm will need to be seen on the day of infusion which should occur within 48 hours of randomization and be within 96 hours of symptom onset.

5.2.1 Day 0. May be done remotely.

- Screening
- Informed consent must be obtained before performing study related activities (can be from healthcare proxy if subject unable to provide consent due to medical status)
- Baseline Evaluation (at screening)
 1. Demographics (age, sex ethnicity, race)
 2. Medical history
 - a. Date of onset of COVID-19 symptoms
 - b. Date of positive test
 - c. Acute and chronic medical conditions described in the eligibility criteria 3.2.
 - d. Charlson Co-morbidity Index calculation
 3. COVID-19 symptom screen (Y/N)
 - a. Fever (T Max)
 - b. Cough
 - c. Shortness of breath
 - d. Ageusia and/or anosmia
 - e. Myalgias
 - f. Headache
 - g. Other symptoms that the patient attributes to their COVID-19 infection
 4. Documentation of positive nasopharyngeal COVID-19 testing.
 5. Determination of eligibility as per inclusion/exclusion criteria
 6. Randomization

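### Entry and Treatment infusion both close at 96 hours from symptom onset with no feasibility check before randomization, and hospitalization is counted from a start of therapy that the two arms do not share

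*Combined protocol and SAP*

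**What the plan says.** **Entry.** Section 3.2 requires a patient "newly diagnosed with a COVID-19 infection with onset of first symptoms" no more than 96 hours ago. It does not say at which moment this is measured. Section 5.2.1 lists the eligibility decision and randomization as consecutive steps of Day 0.

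**Infusion.** Sections 5.2 and 5.2.2 both say that infusion in the Treatment arm "should occur within 48 hours of randomization and be within 96 hours of symptom onset". Section 5.2 also states: "Patients may be screened, enrolled and randomized remotely". A Treatment patient may therefore still have to travel to the site, have blood drawn (including ABO Rh), and receive premedication 30 to 60 minutes before the infusion. The infusion begins at about 50 mL per hour for 30 minutes, after which "the rate may be increased up to 150 mL per hour until completion".

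**Time origin.** Section 5.2 sets a common clock: "The day of randomization will be designated as day 0 for both Treatment and Control groups". The primary endpoint does not use it. Section 8.1 (21 days) and section 8.3.1 (10 days) both count hospitalization from therapy initiation. Which of the two lengths applies is a different question and is not pursued here.

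**The concern.** The 48-hour allowance after randomization suggests that the planners expected some delay, but the entry criterion reserves no time for it. The infusion limit cannot act as an entry check, because it binds only the Treatment arm and only after allocation is known. Some Treatment patients may thus be infused late or not at all. Analysed as randomized, they dilute the effect, in a trial whose rationale (section 1.1) is that passive antibody works best early.

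The time origin is a related but separate matter. Best supportive care has no natural start of therapy, and neither does a Treatment patient who is never infused. If Treatment time starts at infusion and Control time at randomization, an admission between randomization and infusion has a place in the Control count but no clear place in the Treatment count. That would arise whatever the entry window was.

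**Working it through.** **1. The plan's own figures.** Inputs from sections 8.1 and 8.2: 8% against 18%, one-sided 0.05, looks at 51, 102 and 153 per arm, and the tabulated Z bounds with binding futility. Numerical integration over the three stages gives a type I error of 0.050 and power of 0.802 with unpooled variance (0.794 with pooled variance). Binomial simulation gives 0.807. The stated 0.05 and 0.80 are reproduced, with almost no reserve.

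**2. Time left for infusion.** For a patient randomized t hours after onset, time left = min(48, 96 − t).

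| t (hours) | 48 | 72 | 84 | 90 | 96 |
|---|---|---|---|---|---|
| Hours left | 48 | 24 | 12 | 6 | 0 |

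The full allowance exists only up to hour 48. At hour 96 the patient is still eligible and has no time left.

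**3. Time needed, from the protocol's own steps.**

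- *If the infusion must start by hour 96:* premedication takes 0.5–1 h, so the last workable randomization is at hour 95.0–95.5.
- *If it must finish by hour 96:* at the fastest permitted rate, 25 mL runs in the first half hour and the rest at 150 mL per hour. 400 mL takes 0.5 + 375/150 = 3.0 h, and 500 mL takes 0.5 + 475/150 = 3.67 h. With premedication this is 3.5–4.67 h, so the last randomization is at hour 91.3–92.5. These are best-case times, because 150 mL per hour is a ceiling.

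Travel, blood typing and plasma release come on top. The documents give no times for them.

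**4. Share affected and power.** Assumption: randomization times are spread evenly over hours 0–96 or over hours 48–96. Share u = lead time/96 or lead time/48. Treatment rate = 0.08(1 − u) + r·u, with r = 0.18 if affected patients get no benefit. Control stays at 0.18. Power ranges cover integration with unpooled variance and simulation with pooled and unpooled Z.

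| Lead time | Share affected | Power, no benefit |
|---|---|---|
| None | 0% | 0.802–0.807 |
| 0.5–1 h (start by 96 h) | 0.5/96 = 0.5% to 1/48 = 2.1% | 0.785–0.803 |
| 3.5–4.67 h (finish by 96 h) | 3.5/96 = 3.6% to 4.67/48 = 9.7% | 0.716–0.776 |
| 12 h (assumed logistics) | 12/96 = 12.5% to 12/48 = 25% | 0.561–0.693 |

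By share alone, with no benefit in those affected: 5% gives 0.76, 10% gives 0.71–0.72 (Treatment rate 0.08 × 0.9 + 0.18 × 0.1 = 0.09), and 20% gives 0.61–0.62. If affected patients keep half the benefit (r = 0.13), the same shares give 0.78–0.79, 0.76 and 0.71–0.72.

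**5. Time origin.** Time from randomization to the start of therapy, by group:

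- Infused Treatment patients: 0–48 h if the window is kept.
- Uninfused Treatment patients: undefined.
- Control patients: undefined.

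A gap of 48 h is 48/240 = 20% of a 10-day window, or 48/504 = 9.5% of a 21-day window. The documents do not say when admissions are expected within the window, so no effect on the estimate can be computed.

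**The case against.** The strongest reply is that the wording fixes when the patient comes in for infusion, not when the last millilitre runs in. On that reading the protocol's own steps touch 0.5–2% of patients. At 2% the loss of power is about 0.017, much the same as the spread between methods for the undiluted design (0.794 to 0.807). This stands. The larger losses need a finish-by-96 reading or an assumed 12-hour lead, entry times spread evenly up to the limit, and, for the lowest figures, no benefit at all in anyone affected. None of these is in the documents.

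It is also fair to say that hour-level cut-offs are finer than the plan's own resolution, since section 5.2.1 lists the "Date of onset of COVID-19 symptoms". The assessment schedule in Appendix B appears only as a heading and the case report form is not supplied. Whether the hour of onset is recorded is therefore left aside as a matter of detail.

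A third reply is that the time origin is a separate issue and that day 0 is already defined for both arms. The first half is right, and the two are kept apart here. The second half helps the fix rather than the current text: sections 8.1 and 8.3.1 do not refer to day 0.

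A reader might infer that the two limits contradict each other. They do not: both can be met by anyone randomized early enough. A reader might also infer that randomization is biased or that uninfused patients will be dropped. Nothing supports either. Allocation is unaffected, and no section plans such an exclusion, although none names the analysis population for the primary endpoint.

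**Conclusion.** The point holds in a limited form. As written, the plan allows valid randomization to Treatment of a patient who cannot be infused in the window. On the start-of-infusion reading, counting only premedication and with even entry times, the expected cost is negligible: 0.5–2% affected and power of 0.79–0.80. A power of 0.72 or below is an illustration of what slower logistics could do, not a finding about this trial.

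It would be tempting to conclude that the trial is materially underpowered, or that plasma after hour 96 is worthless. The documents support neither. They give no share of late entrants. The infusion limit is worded as something that should happen, so late infusion remains possible. The example in section 1.1 of no benefit after the third day concerns pneumococcal pneumonia.

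The time-origin point does not depend on how many patients enter late. The start of therapy is undefined for the whole Control arm and for uninfused Treatment patients, and can be up to 48 hours after randomization for the rest. The arms therefore share no origin, and Treatment admissions before infusion may be left out. Leaving them out would favour Treatment, by an amount that cannot be sized from the documents.

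**What to change.** 1. Add to section 3.2, for both arms and checked before randomization: 'plasma infusion can be started within 96 hours of symptom onset'.
2. State in section 5.2.2 that the 96-hour limit refers to the start of infusion.
3. In sections 8.1 and 8.3.1, replace therapy initiation with 'randomization (day 0)', and state that all randomized patients are analysed in their assigned arm whether or not they were infused.

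The cost is amendment wording. No change in sample size is needed. A few late presenters become ineligible, so accrual may be slightly slower.

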7.1 Adverse events

7.1.1 Definitions

For the purposes of this Protocol, an AE is defined as any untoward medical occurrence associated with the donation or use of a convalescent plasma for COVID-19 whether or not considered related, that occurs after a subject provides informed consent. Abnormal laboratory values or test results occurring after informed consent constitute AEs only if they induce clinical signs or symptoms, are considered clinically meaningful, or require therapy (eg, hematologic abnormality that requires transfusion).

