7.3 Data Safety Monitoring Board (DSMB)

This study will be approved and monitored by the HackensackUMC DSMB. The DSMB is responsible for the monitoring of investigator initiated research studies to ensure the safety of participants, the integrity of the data, and the appropriate termination of studies in the event that undue risks have been uncovered, or it appears that trials cannot be conducted successfully. The DSMB provides multidisciplinary, independent oversight of research studies conducted by HackensackUMC staff and or affiliates. The DSMB can require protocol modifications related to participant safety and to recommend suspension or termination to the IRB and institutional official of any research protocols that fall within its jurisdiction. The DSMB may request that HackensackUMC's Corporate Compliance Department conduct periodic audits to assure that data are being collected and recorded according to the protocol.

The investigator is required to submit monthly monitoring reports which include current enrollment data, adverse event summary data and any other data requested by the DSMB. The DSMB will meet monthly to review the trial progress, adverse event data, and any relevant information such as significant amendments or reviews from IRB submitted by the principal investigator. If significant concerns are raised by the DSMB, the concerns will be forwarded to the PI as well as recommendations made to the IRB, and Institutional Official. Recommendations may include modifying, suspending, or terminating the protocol.

8. Study Design and Sample Size Considerations

This is a randomized phase II trial to assess the efficacy and safety of treatment with convalescent plasma infusion (Treatment) versus without convalescent plasma infusion (Control) in patients with early COVID-19 infection at high-risk of admission. Eligible subjects will be stratified randomized by their Charlson Comorbidity Index scoring in a 1:1 ratio to receive either Treatment or Control (8.4). For this trial, we have considered a group sequential design which has more interim analyses and utilized a three-stage O'Brien-Fleming design.²³

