8.3.2 Safety Assessment

Safety assessment will be performed on infusion days 0 (post infusion), +3 and +7 days by telephone (closest business day is acceptable), +2 weeks (+/- 3 days), +4 weeks (+/- 3 days), 2 months (+/- 5 days). The safety of the trial will be accessed by evaluating the therapies exposure, adverse events (AE), and

death. Adverse events that begin or worsen after initiation of plasma donation or infusion should be recorded on the Adverse Events Form of the CRF.

A summarization of the number of days and/or cycles subjects were exposed to the therapies will be provided. AE (and serious adverse events, SAE) will be graded and recorded throughout the study and during the follow-up period according to the NCI Common Terminology for Adverse Events (CTCAE) v4.03. Toxicities will be characterized in terms regarding seriousness, causality, toxicity grading, and action taken with regard to trial treatment. The percentage of subjects experiencing an adverse event at a given severity, an NCI CTCAE toxicity grade, and the relationship to study therapy, will all be provided. And the number of subject deaths throughout the study will be summarized.

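### Infusion-day monitoring reaches only infused patients and 8.3.2 has no rule for what it finds, so a crude by-arm AE percentage is likely, though not certain, to be inflated for plasma

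*Combined protocol and SAP*

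**What the plan says.** Section 8 (opening paragraph) says the trial will "assess the efficacy and safety of treatment with convalescent plasma infusion (Treatment) versus without convalescent plasma infusion (Control"). Section 8.3.2 then plans descriptive summaries, including "The percentage of subjects experiencing an adverse event at a given severity", CTCAE grade and relationship to therapy. It does not say that these are by arm, and it plans no AE test.

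For infused patients, 5.2.2 states "On the day of infusion, blood will be drawn for" D-dimer, ferritin, CRP, antibody titer, CBC, complete chemistry and ABO/Rh, and it sets the vital-sign schedule "Temperature, pulse, respirations, and blood pressure pre-infusion (within 30 minutes), 15 minutes after the start, every hour during", plus a post-transfusion set. For both arms the enrollment contact is "5.2.1 Day 0. May be done remotely" and the next two are "Post enrollment day +3 and day +7 (or closest working day). May be done remotely". The visits at 2 weeks, 4 weeks and 2 months (5.2.4) are preferably in person. Under 5.2.5, a hospitalized Control may receive plasma and then follows 5.2.2.

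On what counts as an AE, 7.1.1 says "Abnormal laboratory values or test results occurring after informed consent constitute AEs only if they induce clinical signs or symptoms, are considered clinically meaningful" or need therapy. Section 7.1.2 accepts AEs detected by examination, laboratory test or other assessment. Section 6.3.1 monitors AEs from consent and records them whatever the assumed cause, whereas 7.1.2 and 8.3.2 record those that start or worsen after infusion begins.

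**The concern.** An AE percentage depends on how hard one looks. Treatment patients are observed for several hours with repeated temperature, pulse, respiration and blood-pressure readings, within 96 hours of COVID-19 onset. Section 1.3 lists fever, tachycardia and blood-pressure changes among plasma effects, but early COVID-19 can plausibly produce the same signs. A never-infused Control with the same transient finding that day has no scheduled reading to reveal it. If both arms' AE percentages are then set side by side, part of any excess in Treatment may reflect the extra looking. There is also no Control background rate for the infusion day against which to judge attribution.

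**Working it through.** The plan states no AE rate and no safety precision, so there is no figure of its own to reproduce. The check compares the schedules and then illustrates size under stated assumptions.

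**1. Scheduled observation**

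| Contact | Treatment | Control, never infused |
|---|---|---|
| Day 0 (5.2.1) | History, symptom screen with maximum temperature; no bloods or vital signs listed | Same |
| Infusion day (5.2.2) | Blood panel, serial vital signs, post-infusion safety assessment (2.4) | No contact |
| +3, +7 (5.2.3) | Symptom screen with maximum temperature, AE and safety questions | Same |
| 2 weeks, 4 weeks, 2 months (5.2.4) | Same questions; titers if possible; COVID-19 swab at 2 weeks, repeated at 4 if positive; no CBC, chemistry or vital signs listed | Same |

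The arms differ only in the infusion-day row.

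**2. Amount of extra observation.** By 5.2.2, the first 30 minutes run at 50 mL/h (25 mL), then at up to 150 mL/h. Shortest time = 0.5 + (V − 25)/150 hours.
- V = 400 mL: 0.5 + 375/150 = 3.0 h.
- V = 500 mL: 0.5 + 475/150 = 3.7 h.

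Vital-sign sets: 1 before, 1 at 15 minutes, 2 to 3 hourly, 1 after, so about 5 to 6. The extra looking covers hours, not weeks.

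**3. Which findings can become AEs**
- *Vital signs during and after infusion.* A change that begins or worsens here satisfies both 6.3.1 (from consent) and 7.1.2/8.3.2 (after infusion starts). This is the main route.
- *Blood panel.* There is one draw. The titer is stated to be pre-infusion (2.2, 8.3.3), and the rest is plausibly taken with it. An abnormality present before infusion falls outside 7.1.2/8.3.2 but inside 6.3.1. No repeat CBC or chemistry is listed. This route is weak and depends on which rule governs.

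**4. Illustrative size.** From the documents: n = 153 per arm (8.2). Assumed: b, the share with an AE from the shared contacts, is equal in both arms; plasma does no harm; q is the share of otherwise AE-free Treatment patients who gain an AE only through infusion-day monitoring.

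Treatment percentage: p_T = b + (1 − b)q. Control: p_C = b.
Chance that a 95% Wald interval for the difference lies wholly above zero: Φ[(p_T − p_C)/SE − 1.96], with SE = √{[p_T(1 − p_T) + p_C(1 − p_C)]/153}. The nominal value is 2.5%.

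Example, b = 0.30 and q = 0.10: p_T = 0.30 + 0.70 × 0.10 = 0.37; SE = √[(0.2331 + 0.2100)/153] = 0.0538; Φ(0.07/0.0538 − 1.96) = 25.5%.

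Each cell gives p_T, then the chance of a false harm signal:

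| b | q = 2% | q = 5% | q = 10% | q = 20% |
|---|---|---|---|---|
| 10% | 11.8%; 7.3% | 14.5%; 22.5% | 19.0%; 61.6% | 28.0%; 98.5% |
| 20% | 21.6%; 5.3% | 24.0%; 13.3% | 28.0%; 37.7% | 36.0%; 88.6% |
| 30% | 31.4%; 4.5% | 33.5%; 9.6% | 37.0%; 25.5% | 44.0%; 72.7% |
| 40% | 41.2%; 4.0% | 43.0%; 7.7% | 46.0%; 18.5% | 52.0%; 56.4% |

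The plan contains no such interval. The probabilities only scale what a reader comparing two percentages could be led to conclude.

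**The case against.** Close monitoring is inherent in an open infusion-versus-no-infusion trial, and 8.3.2 already reports relationship to therapy. The safety endpoint in 2.4 is AEs associated with infusion, and no between-arm AE test is planned. That stands, but Section 8 still frames safety as Treatment versus Control, and two arm percentages will be compared.

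The direction is not proven. Premedication in 5.2.2 (hydrocortisone, optionally acetaminophen and diphenhydramine) may mask fever or allergic signs. Under the design rates of 8% and 18% (8.1), more Controls would be in hospital under closer observation. Both work against the inflation.

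Four stronger readings are tempting, and the documents do not support them.
- *Only Treatment patients are monitored, throughout the first two weeks.* There is one draw and a few hours of readings, and Controls given plasma in hospital get both. At the assumed 18%, 0.18 × 153 ≈ 28 Controls would be hospitalized; how many would receive plasma is unknown.
- *Fever is measured in Treatment only.* Maximum temperature is on the symptom screen for both arms at every shared contact, and 7.1.2 accepts AEs volunteered between visits.
- *Treatment has six AE occasions against five.* Section 7.1.2 also seeks AEs on day 0 from all recipients, which makes it 7 against 6, or 6 against 6 if infusion falls on day 0.
- *Controls certainly have no tests.* The content of Appendix B, the recipient schedule, is not in the text, so tests listed there cannot be excluded.

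Finally, removing non-serious infusion reactions from the main comparison would hide the most direct plasma harm. That objection is sound, so the fix keeps them in.

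**Conclusion.** The point holds in a limited form. AE ascertainment differs between infused patients and never-infused Controls on the infusion day, the extra findings can qualify as AEs, and 8.3.2 does nothing to separate them. Inflation of the crude Treatment percentage is likely, not certain. A reader might infer that the AE percentages are definitely biased against plasma; the masking and hospital-observation effects, and the absence of a specified comparison, rule out that certainty.

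The size is unknown. Across assumed base rates of 10% to 40%, it runs from 1.2 to 1.8 percentage points at 2% extra detection to 12 to 18 points at 20%. Nothing in the documents fixes where the trial would fall. The efficacy design is unaffected. The change is worth making because it is cheap and loses no harm data.

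**What to change.** Amend 8.3.2, with matching wording in 6.3.1 and 7.1.2:

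1. Reconcile the AE recording rules. Laboratory results drawn before infusion on the infusion day, and pre-infusion vital signs, are baseline values; only later worsening counts as an AE.
2. Keep the full by-arm AE table with infusion reactions included. Beside it, add a by-arm table of AEs elicited at the contacts common to both arms (+3, +7, 2 weeks, 4 weeks, 2 months), plus all SAEs and deaths from randomization.
3. Tabulate AEs found at the infusion visit, including transfusion reactions, separately for infused patients.

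The cost is plan wording and two extra tables, with no new visits, tests or patients. The downside is that the common-contact table omits non-serious infusion-day reactions, so it must never be shown or read without the other two.
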